It is recognized that the major disruption involving Ukraine, Russia, and neighboring countries/territories may have an impact on the conduct of this clinical study due to, for example, isolation or quarantine of participants and study site personnel; travel restrictions/limited access to public places, including hospitals; study site personnel being unavailable, isolated, or reassigned to critical tasks.

The sponsor is providing options for study related participant management in the event of disruption to the conduct of the study. This guidance does not supersede any local or government requirements or the clinical judgement of the investigator to protect the health and well-being of participants and site staff. If, at any time, a participant's travel to the study site is considered to be dangerous, study participation may be interrupted, and study follow-up conducted. If it becomes necessary to discontinue participation in the study, the procedures outlined in the protocol for discontinuing study intervention will be followed.

If, as a result of the major disruption involving Ukraine, Russia, and neighboring countries/territories scheduled visits cannot be conducted in person at the study site, they will be performed to the extent possible remotely/virtually or delayed until such time that on-site visits can be resumed. At each contact, participants will be interviewed to collect safety data. Key efficacy endpoint assessments should be performed if required and as feasible. Participants will also be questioned regarding general health status to fulfill any physical examination requirement.

Every effort should be made to adhere to protocol-specified assessments for participants on study intervention, including follow up. Modifications to protocol-required assessments may be permitted after consultation with the participant, investigator, and the sponsor.

The sponsor will continue to monitor the conduct and progress of the clinical study, and any changes will be communicated to the sites and to the health authorities according to local guidance. Modifications made to the study conduct as a result of the major disruption involving Ukraine, Russia, and neighboring countries/territories should be summarized in the clinical study report.

- Certain protocol-mandated visits to the study site may not be possible during the major disruption involving Ukraine, Russia, and neighboring countries/territories. Therefore, temporary measures may be implemented if considered appropriate by the sponsor and investigator to maintain continuity of patient care and study integrity. Certain measures, such as those listed below, may be necessary and should be instituted in accordance with applicable (including local) laws, regulations, guidelines, and procedures:
 - remote (eg, by phone/telemedicine) or in person, off-site (eg, in-home) interactions between site staff (or designees) and participants for study procedures eg, those related to safety monitoring/efficacy evaluation/study intervention storage and administration (including training where pertinent)

- study intervention administration may take place outside of the scheduled visit window, if the investigator determines this to be safe for the participant, due to disruption of study intervention shipment to the site
- laboratory assessments using a suitably accredited local laboratory
- Missed assessments/visits will be captured in the clinical trial management system for protocol deviations. Discontinuations of study interventions and withdrawal from the study should be documented in the electronic case report form (eCRF).
 - other relevant study data elements impacted by the major disruption involving Ukraine, Russia, and neighboring countries/territories should also be documented in eCRFs and/or other study systems, as directed by detailed sponsor guidance. These may include missed/delayed/modified study visits/assessments/dosing, and instances where temporary measures such as those above are implemented.
- The sponsor will evaluate the totality of impact of the major disruption involving Ukraine, Russia, and neighboring countries/territories on collection of key study data.
 - if needed additional data analyses will be outlined in study statistical analysis plan.

INVESTIGATOR AGREEMENT

I have read this protocol and agree that it contains all necessary details for carrying out this study. I will conduct the study as outlined herein and will complete the study within the time designated.

1.0	13 August 2020	Not Applicable	Initial release, draft approved for dossier use
2.0	16 August 2022	All sections: Added and/or modified text at the beginning of sections and subsections to clarify changes in the statistical analysis plan due to early study termination, and to clarify the analyses that will be included in the CSR.	Statistical analysis plan is changed due to early termination of the study
		Section 1.2: Minor updates on study design per protocol; Section 5.1: Removed baseline definition for proteinuria as the general baseline definition will be used; Section 5.2: Updated the timepoint for disposition summary; Section 5.4.2.2.7.1: Updated ICEs for the main estimand for time to achievement of CRR; Section 5.4.2.3: Updated analysis method for Secondary Endpoint 2. Section 5.5.1: Minor updates on definition of endpoints for clarity; Section 5.6: Minor updates in analysis methods. Section 5.7: Minor edits for clarity.	Minor updates for clarification

1. INTRODUCTION

This Statistical Analysis Plan (SAP) contains definitions of analysis sets, derived variables, and statistical methods for all planned analyses of efficacy, safety, tolerability, pharmacokinetics (PK), pharmacodynamics (PD) and immunogenicity of guselkumab. This SAP incorporates all analyses through the final database lock (DBL) for the CNT01959LUN2001 study.

Early Termination Note: The original study design included a target of approximately 60 participants to be randomly assigned with approximately 30 participants planned per intervention group. Due to the Sponsor's decision to stop screening of new participants as a result of enrollment challenges, fewer than 60 participants will be enrolled in the study. The end of study will occur after all enrolled participants have completed the Week 20 visit or discontinued study intervention prior to Week 24, and all participants have completed their final efficacy and safety visits per the Schedule of Activities (SoA).

There will be only one database lock that will occur at the end the study. All data through the end of the study including the long term extension (LTE) data will be summarized together. Analyses that will be performed and included in the abbreviated Clinical Study Report (CSR) are noted below at the beginning of each respective section. The analyses not performed will be retained in this SAP for completeness.

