5.1.1. Long-Term Extension Inclusion Criteria

Each potential participant must satisfy the following criteria to continue to receive study intervention as part of the LTE:

1. The participant has achieved CRR at Weeks 48 and 52 and has completed the Week 52 assessments per [Table 2](#) of the SoA (Section 1.3).
2. Must sign an ICF indicating that he or she understands the purpose of, and procedures required for, the LTE and is willing to participate in the LTE. (In regions where the legal age of consent is older than 18 years, those under the legal age, must obtain signed informed consent from both the participant and his or her legally acceptable representative.)
3. In the judgement of the study Investigator, the participant must be suitable for inclusion in the LTE portion of the study.

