9.4.6. Safety Analyses

All safety analyses will be analyzed using the SAS population (refer to Section 9.3 for definition).

Adverse Events

The verbatim terms used in the eCRF by investigators to identify AEs will be coded using the Medical Dictionary for Regulatory Activities. Any AE occurring at or after the initial administration of study intervention is considered to be treatment-emergent. All reported treatment-emergent AEs will be included in the analysis. For each AE, the percentage of participants who experience at least 1 occurrence of the given event will be summarized by intervention group. In addition, comparisons between intervention groups will be provided if appropriate.

The following analyses of AEs will be used to assess the safety of participants:

- Frequency and type of AEs.
- Frequency and type of SAEs.
- Frequency and type of reasonably related AEs as assessed by the investigator.
- Frequency and type of AEs leading to discontinuation of study intervention.
- Frequency and type of infections, serious infections, and infections requiring oral or parenteral antimicrobial treatment.
- Frequency and type of AEs temporally associated with an infusion.
- Frequency and type of injection-site reactions.

Summaries, listings, datasets, or participant narratives may be provided through Week 24 and Week 60 by treatment intervention, for the above AEs, deaths, and severe AEs. Selected safety summaries will also be performed for participants of the LTE (Section 9.4.8).

Clinical Laboratory Tests

Laboratory data will be summarized by type of laboratory test over time, and by treatment intervention. CTCAE toxicity grades (specified in the SAP) will be used in the summary of laboratory data. Descriptive statistics will be calculated for each laboratory analyte at baseline and for observed values and changes from baseline at each scheduled timepoint.

The following summaries of clinical laboratory tests will be used to assess participant safety:

- Laboratory parameters and change from baseline in laboratory parameters (hematology and chemistry).
- Summary of maximum CTCAE toxicity grade for postbaseline laboratory values (hematology and chemistry).

Listings of participants with any abnormal postbaseline laboratory values of CTCAE Grade ≥ 2 will also be provided.

Vital Signs

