9.4.8. Long-Term Extension

The LTE begins after the assessments have been completed at Week 52, and will continue until end of study (see Section 4.1.3).

The objective of the LTE is to evaluate the efficacy and safety of long-term guselkumab treatment.

Assessments during the LTE described below will be summarized by treatment group as specified in the SoA (Section 1.3) if data permits:

- Selected efficacy assessments including proportion of participants maintaining CRR through Week 152.

- Changes in PRO assessments including LupusQOL, FACIT-Fatigue, lupus symptoms, and PGIC over time during the long-term extension.
- Selected safety data including analyses of AEs, clinical laboratory tests, and vital signs.
- Serum guselkumab concentrations and antibodies to study intervention.
- Selected biomarkers.

Details of the analyses planned for the LTE will be described in the SAP.

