5.7. Safety Analyses

Early Termination Note: Due to the Sponsor's decision to stop screening of new participants as a result of enrollment challenges, fewer than 60 participants will be enrolled in the study. The end of study will occur after all enrolled participants have completed the Week 20 visit or discontinued study intervention prior to Week 24, and all participants have completed their final efficacy and safety visits per the SoA.

For the CSR, all safety analyses described below will be performed on all available data through the end of study.

All safety analyses will be based on the safety analysis set based on actual intervention received, unless otherwise specified.

For all continuous safety variables, descriptive statistics by intervention group will include the N, mean, SD, median, minimum, and maximum. Categorical variables will be summarized by intervention group using frequency counts and percentages.

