5.7.2. Adverse Events

The verbatim terms used in the case report form by investigators to identify AEs will be coded using the Medical Dictionary for Regulatory Activities (MedDRA). Any AE occurring at or after the initial administration of study intervention is considered to be treatment emergent. If the event occurs on the day of the initial administration of study intervention, and either event time or time of administration are missing, then the event will be assumed to be treatment emergent. If the event date is recorded as partial or completely missing, then the event will be considered to be treatment emergent unless it is known to be prior to the first administration of study intervention based on partial onset date or resolution date. All reported treatment-emergent AEs will be included in the analysis. For each adverse event, the number and percentage of participants who experience at least 1 occurrence of the given event will be summarized by intervention group.

Summary tables and listings will be provided for treatment-emergent AEs:

- AEs
- Serious AEs (SAEs)
- AEs by severity, NCI-CTCAE toxicity grade
- AEs reasonably related to study intervention
- Had AEs leading to discontinuation of study intervention/termination of study participation

Summaries and listings of other treatment-emergent AEs of special interest will be provided. These include infections, serious infections, opportunistic infections, malignancies, hypersensitivity reactions, tuberculosis, AEs related to COVID-19, injection-site reactions, and AEs temporally associated with infusions.

Deaths will be displayed by actual study intervention received. A listing of study participants who died will be provided.

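### AE and maximum-toxicity-grade percentages pool responder-only LTE follow-up with no common window, and the protocol's LTE safety summaries are missing from the SAP (minor)

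*SAP*

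**What the plan says.** **Pooling.** The early-termination note in SAP Section 1 states "All data through the end of the study including the long term extension (LTE) data will be summarized together". The note heading SAP 5.7 says that, for the CSR, "all safety analyses described below will be performed on all available data through the end of study".

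**AE measure.** Under SAP 5.7.2, for each event, "the number and percentage of participants who experience at least 1 occurrence of the given event will be summarized by intervention group". Treatment emergence has a start but no end: "Any AE occurring at or after the initial administration of study intervention is considered to be treatment emergent". No AE rate is planned. Maximum toxicity grade in SAP 5.7.3.1 is also a proportion by arm over all post-baseline values. By contrast, laboratory changes are windowed at Weeks 24 and 52 (SAP 5.7.3.1) and vital-sign changes at Weeks 24 and 60 (SAP 5.7.3.3).

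**Who enters the LTE.** The first criterion in Protocol 5.1.1 is "The participant has achieved CRR at Weeks 48 and 52". Protocol 6.1.1 keeps each entrant on the assigned treatment, so both arms can contribute.

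**What the protocol planned.** Protocol 9.4.6: "Selected safety summaries will also be performed for participants of the LTE". Protocol 9.4.8: "Assessments during the LTE described below will be summarized by treatment group", subject to the data permitting it. The items listed there include "Selected safety data including analyses of AEs, clinical laboratory tests, and vital signs", with details left to the SAP. Protocol 9, as revised for early termination, keeps all safety analyses. The SAP has no LTE safety summary and no LTE analysis set. Its Appendix 2, which is meant to list changes from protocol-planned analyses, says not applicable.

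**The concern.** A crude percentage with at least one event rises with time observed. Participants outside the LTE have a final safety visit at Week 60 or earlier, while LTE entrants are observed for longer. LTE entry depends on CRR, a major secondary efficacy endpoint that the drug is hypothesised to improve. If more of one arm enters, that arm collects more first events even when the event hazard is the same in both arms. The AE tables are descriptive, but columns set side by side will be read as a safety comparison.

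The separate LTE summary planned in the protocol would have shown which events arose in the extension. Without it, and without a common window, the planned tables do not separate risk from observation time.

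**Working it through.** **Inputs.** The documents give no figure to reproduce, so the rates below are assumptions.

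- Event hazard λ, equal in both arms: 0.2, 0.5 or 1.0 per year (assumed).
- CRR among those reaching Week 52: 40% vs 15%, or 30% vs 10% (assumed).
- LTE follow-up beyond Week 60: spread evenly over 0 to 60 weeks. SAP 5.9 dates the first interim at 28 December 2021, and SAP 5.9.1 places it 2 months before the first LTE entry, so about 28 February 2022. Eight weeks later (Week 60) is 25 April 2022. Taking SAP version 2.0 (16 August 2022) as the latest screening start and adding 12 weeks of screening, 20 weeks to the last dose and 12 weeks of safety follow-up gives 20 June 2023. The difference is 60.1 weeks.
- Number reaching Week 52: about 25 (assumed). SAP 5.9 says the second interim, due at about 25 Week 24 completers, will not be held. That suggests small numbers but does not fix them, and the result scales in proportion.
- Everyone else is treated as balanced between arms.

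**Step 1: extra probability of a first event per LTE entrant.** F(t) = 1 − exp(−λt/52). The increment is the mean of F over 60 to 120 weeks, minus F(60).

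| λ per year | F(60) | mean F, 60–120 | increment |
|---|---|---|---|
| 0.2 | 0.206 | 0.291 | 0.085 |
| 0.5 | 0.438 | 0.573 | 0.135 |
| 1.0 | 0.685 | 0.813 | 0.128 |

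**Step 2: about 25 participants reaching Week 52.** With 12.5 per arm, 40% vs 15% gives 12.5 × 0.25 = 3.1 extra entrants. Multiplying by the increments gives 0.27, 0.42 and 0.40 of an extra participant with an event.

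**Step 3: wider range at 30 per arm.** Gap = q × (CRR difference) × increment, with q the share reaching Week 52.

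- Smallest: 0.25 × 0.20 × 0.085 = 0.42 points, or 0.13 of a participant.
- Largest: 0.75 × 0.25 × 0.135 = 2.53 points, or 0.76 of a participant. This needs 45 of 60 people to reach Week 52.
- Equal CRR: zero.

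**Step 4: does a participant-year rate remove the gap?** Only if the hazard is constant. Take λ = 0.5 to Week 60 and half that afterwards, q = 0.5, CRR 40% vs 15%.

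- Extra event probability per entrant: 0.562 × (1 − 0.869) = 0.074. Here 0.562 is the chance of being event-free at Week 60, and 0.869 is the mean chance of staying so over the extra 0 to 60 weeks.
- Crude: 0.438 + 0.5 × 0.40 × 0.074 = 45.3%, against 0.438 + 0.5 × 0.15 × 0.074 = 44.4%. Ratio 1.02.
- Person-years to first event: 0.438/0.5 = 0.877 up to Week 60, plus 0.074/0.25 = 0.295 per entrant. Rates: 0.4531/0.9358 = 48.4 against 0.4439/0.8989 = 49.4 per 100 participant-years. Ratio 0.98.

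The rate reverses the gap by about the same amount.

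**Step 5: cost of a Week 24 window.** At λ = 0.5, F(24) = 20.6% against F(60) = 43.8%.

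**The case against.** **The pooling is disclosed.** A reader might infer that the LTE view was dropped without saying so. The documents do not support that: SAP Section 1 states the pooling in a note on early termination, and the version history attributes the changes to it. Protocol 9 also allows some analyses to be omitted, and 9.4.8 is conditional on the data. What stands is narrower. Protocol 9.4.6 is unconditional, Protocol 9 keeps all safety analyses, and the SAP neither plans the LTE summary nor lists its omission in Appendix 2.

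**The effect is too small to see.** At 30 per arm and 44% incidence, the standard error of a between-arm difference is √(2 × 0.438 × 0.562 / 30), or about 12.8 points, against a gap of 0.4 to 2.5 points. SAP 5.7 plans no safety tests. This stands and is why the point is minor.

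**The SAP has mitigations.** SAP 5.7.1 gives participant-weeks by arm, SAP 5.7.2 plans AE listings, and SAP 5.1.3 gives each safety assessment a study day. With about 3 extra entrants, late events could be traced one by one. That helps, but the participant-weeks run from first to last dose (48 of 60 weeks for a main-study completer) and are not tied to AE counts. SAP 5.1 mentions Week 0 to Week 60, but SAP 5 says the note heading each section governs the CSR.

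**Early withdrawal also unbalances follow-up.** True of any cumulative AE table, and it could offset the LTE effect. It does not come from LTE pooling and is not counted here.

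**Conclusion.** The point holds as a minor one. The pooled AE and toxicity-grade percentages depend on length of observation, and the LTE part of that length depends on CRR. This follows from the stated rules. Its size rests wholly on assumed rates: about 0.3 to 0.4 of a participant if about 25 reach Week 52 with CRR of 40% vs 15%, and nothing if CRR is equal by arm. The mismatch between Protocol 9.4.6/9.4.8 and the SAP needs no assumption.

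Two stronger readings are not supported. One is that the two-year LTE design implies a gap of 5 to 10 points. Such figures need 100 extra weeks of follow-up, whereas the SAP dates allow about 60 weeks at most for the earliest entrant. The other is that the tables will be biased against guselkumab. The direction depends on which arm has more CRR, which the documents do not give.

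Infusion-associated AEs (infusions only at Weeks 0, 4 and 8) and the windowed laboratory and vital-sign change summaries are not affected.

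**What to change.** 1. Make the between-arm comparison of AEs and maximum toxicity grade a table through Week 24, and keep the all-data table as descriptive. Protocol 9.4.6 already allows AE summaries through Weeks 24 and 60. Under the end-of-study rule and footnote c of Schedule of Activities Table 1, every participant has the opportunity to reach Week 24. This removes the LTE effect from the comparison.
2. Add the LTE safety summary by treatment group to SAP 5.7, or record its omission and the reason in Appendix 2.
3. If an incidence per 100 participant-years is wanted, add it only as a supplement, with follow-up counted to last contact rather than last dose. State that it assumes a constant hazard and can favour the arm with more LTE entrants if their later hazard is lower.

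The cost is SAP wording and a few tables from data already collected. The real downside is fewer events in the window: about 21% of participants with an event by Week 24 against 44% by Week 60, at an assumed 0.5 events per year.

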1.1. Objectives and Endpoints

Due to the Sponsor's decision to terminate the study early, only the primary endpoint, major secondary endpoints, and safety endpoints will be reported in the CSR. Details will be described in each respective section.

For informational purposes, the below table outlines the objectives and endpoints originally planned for the study.

Objectives	Endpoints
Primary	

 To evaluate the efficacy of guselkumab in participants with active lupus nephritis (LN) 	
Primary endpoint: Proportion of participants achieving at least 50% decrease in proteinuria from baseline at Week 24
 
Secondary endpoints to include:
 
 Proportion of participants achieving complete renal response (CRR) at Week 24 Proportion of participants achieving a sustained reduction in steroid dose ≤ 10 mg/day of prednisone or equivalent from Week 16 to Week 24 Proportion of participants achieving at least 50% decrease in proteinuria from baseline at Week 52 Proportion of participants achieving CRR at Week 52 Proportion of participants with Urine Protein to Creatinine Ratio (UPCR) < 0.5 mg/mg at Week 24

Objectives	Endpoints
	
 • Proportion of participants with UPCR <0.75 mg/mg at Week 24 • Time to achievement of CRR • Time to treatment failure (TF)
Secondary	

 • To evaluate the safety and tolerability of guselkumab in participants with active LN 	
 • Frequency and type of adverse events (AEs), serious adverse events (SAEs), reasonably related AEs, AEs leading to discontinuation of study intervention, infections, serious infections, and infections requiring oral or parenteral antimicrobial treatment, AEs temporally associated with an infusion, and injection-site reactions • Laboratory parameters and change from baseline in laboratory parameters (hematology and chemistry) • Summary of maximum Common Terminology Criteria for Adverse Events (CTCAE) toxicity grade for postbaseline laboratory values (hematology and chemistry) • Systolic and diastolic blood pressures over time

 • To evaluate the PK, immunogenicity, in participants with active LN 	
 • Serum guselkumab levels over time • Serum anti-guselkumab antibodies through Week 24, through Week 52, and in participants discontinuing study intervention early
Tertiary/Exploratory	

 • To evaluate the efficacy of guselkumab in extrarenal lupus manifestations 	
 • Proportion of participants with ≥ 4-point improvement at Week 24 in systemic lupus erythematosus disease activity index 2000 (SLEDAI-2K) modified to exclude renal items • Proportion of participants with baseline arthritis (with at least 4 active joints at baseline) who have $\geq 50\%$ reduction in active joints at Week 24 • Proportion of participants with baseline active mucocutaneous lupus manifestations (CLASI score ≥ 8) and $\geq 50\%$ reduction in Cutaneous Lupus Erythematosus Disease Area and Severity Index (CLASI) scores at Week 24

 • To evaluate the impact of guselkumab on Health-Related Quality of Life (HRQoL) and fatigue in participants with active LN 	
 • Change from baseline in Lupus Quality of Life (LupusQoL) individual domains at Week 24 • Change from baseline in Functional Assessment of Chronic Illness Therapy (FACIT)-fatigue score at Week 24 • Change from baseline in lupus symptoms (joint pain, joint stiffness, rash, and swelling [peripheral edema]) at Week 24 • Patient Global Impression of Change (PGIC) - Change in LN (health condition) at Week 24 and Week 52

Objectives	Endpoints

 To evaluate biomarkers of LN, pharmacodynamic (PD) effects of guselkumab, and to identify participants most likely to benefit from treatment with guselkumab 	
 Serum biomarkers including IL-23, IL-17A, IL-17F, IL-22, complement (C)3, C4, C1q, or autoantibodies, eg, anti-dsDNA Cellular (urine and peripheral blood mononuclear cell [PBMC]) and whole blood gene expression Urine biomarkers (protein and /or nucleic acids)

 Perform analyses of pre- and post-treatment renal biopsies (optional) 	
 Histopathology of glomeruli and tubulointerstitial tissue, immunohistochemistry for resident and infiltrating cell types and inflammatory mediators (including IL-23, IL-17, IL-21, interferon-gamma, chemokines), and/or tissue gene expression

